Title of Study: Cognitive-Communication Screening and Early Therapy for Adults with Concussion/Mild Traumatic Brain Injury

Document Date: 09/13/2016

Type of Document: Study Protocol and Statistical Analyses

Procedures and Statistical Data Analyses: Patients will be evaluated for a concussion/mild traumatic brain injury at a local hospital in the emergency room. On the same day discharge papers, the patient will receive a description about the study and the PI contact information. During hospital follow-up phone calls to check on the status of the patients, they will be reminded of the study being conducted at the university and given the inclusionary/exclusionary criteria.

Subjects that voluntarily contact the PI and meet the inclusionary criteria will be scheduled for cognitive and communication screening at two weeks post-injury. The informed consent will be reviewed and signed prior to beginning the study. All subjects will receive monetary incentives for participation in the screening sessions.

The PI and her research assistants will audiotape all sessions to ensure that subjects' responses are scored and transcribed correctly. Inter-rater reliability of the scored items will be completed for 50% of the screenings conducted. All recordings will be destroyed one week following the sessions. The recordings will be restricted only to the PI and graduate research assistants. Next, the screening measures will be completed, and an education fact sheet will be reviewed with an emphasis on recovery.

At four weeks post-injury, the second screening session will be completed. Subjects who are below one standard deviation on screening scores will be randomly placed in either early treatment at one month post-injury or a waitlist control group which will receive the same therapy at two months post-injury. Subjects offered cognitive-communication therapy will participate in a one hour weekly session for four weeks. Prior to beginning therapy, a functional outcome measure will be administered. Intervention will consist of evidence-based therapies for working memory, executive function, and divided attention, environmental changes, and identification of problematic cognitive-communication situations. At the end of therapy, the same outcome measure will be completed.

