Procedures for therapy will be the same for the waitlist control group. However, during the one month waiting period following the second screening, subjects will be given other activities that differ from the actual therapy activities.

All subjects will be contacted via phone at six months and 12 months post-injury to ensure resolution of cognitive-communication problems. If problems are identified later in recovery, the subjects will be instructed to contact their primary care physician for further referrals.

This is a longitudinal clinical study. Subjects will be followed for one year post-injury. Results from the screening measures at two and four weeks post-injury will be compared using a forward stepwise selection model procedure to determine which of the screening measures best detect persistent symptoms.

Finally, one tailed, non-paired t-tests will be used to compare pre- and post-therapy functional outcomes. Additionally, qualitative analyses will be completed on data related to the treatment.

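### Read literally, the plan tests pre- and post-therapy scores from the same subjects with a non-paired t-test, and it does not name the contrast being tested

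*Combined protocol and SAP*

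**What the plan says.** All the relevant text is in the section Procedures and Statistical Data Analyses.

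- **Measurement (fourth paragraph).** For subjects offered therapy: "Prior to beginning therapy, a functional outcome measure will be administered". After the four weekly sessions: "At the end of therapy, the same outcome measure will be completed".
- **Arms (fourth paragraph).** Subjects who screen below the cut-off at four weeks are "randomly placed in either early treatment at one month post-injury or a waitlist control group"; the latter is the "waitlist control group which will receive the same therapy at two months post-injury".
- **Waitlist arm (paragraph on the waiting period).** "Procedures for therapy will be the same for the waitlist control group", so this arm also has a score before and a score after therapy. No functional measurement at the start of the waiting month is described.
- **Analysis (final paragraph).** "one tailed, non-paired t-tests will be used to compare pre- and post-therapy functional outcomes".

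That last sentence is the only inferential statement about the functional outcome. The other analysis of treatment data is qualitative. The plan gives no sample size, alpha, SD, effect size or pre-post correlation for this outcome, and it names no arm or time point for the tests.

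**The concern.** Two scores from one person on one instrument are normally positively correlated. An independent-samples test assumes they are not correlated at all, so it charges the comparison with between-subject variation that the design removes. If the sentence is carried out as written, p-values will be too large and confidence intervals too wide, and a real change in functional outcome may be missed. Because no other test is stated for this outcome, nothing else in the plan would recover the lost information.

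The second part is that the contrast is left open. The sentence could mean change within subjects (by arm or pooled), a difference between arms in change, or a difference between arms at a common time. These answer different questions and need different tests. A pre-post contrast, however it is tested, also includes natural recovery after concussion.

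**Working it through.** The plan has no figure of its own to reproduce, so the check sets out what the stated test does to paired data.

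**Inputs.** From the documents: the same measure is taken before and after therapy in the same subjects, and the tests are one-tailed and non-paired. Assumed, because the documents are silent: one-sided alpha 0.05, normal scores, equal SD σ at both times, r = 0.3, 0.5 or 0.7, mainly 20 pairs, and a true change of d = 0.5 SD with variations.

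**1. Standard error of the mean change with n subjects.**
- Non-paired test: √(2σ²/n)
- Correct for pairs: √(2σ²(1−r)/n)
- Ratio: 1/√(1−r)

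| r | 0 | 0.3 | 0.5 | 0.7 |
|---|---|---|---|---|
| SE too large by a factor of | 1.00 | 1.20 | 1.41 | 1.83 |

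This step needs only r and equal variances. A negative r would reverse the direction (ratio 0.91 at r = −0.2).

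**2. Actual type I error of the non-paired test, for the null of no change.** The large-sample formula is 1 − Φ(1.645/√(1−r)). The 20-pair figures are simulated, with 200,000 bivariate normal runs per cell.

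| r | Large-sample | 20 pairs |
|---|---|---|
| 0.3 | 1 − Φ(1.966) = 2.5% | 2.6% |
| 0.5 | 1 − Φ(2.326) = 1.0% | 1.2% |
| 0.7 | 1 − Φ(3.003) = 0.1% | 0.2% |

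The paired test stays at about 5% throughout.

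**3. Power.** Non-paired by simulation; paired exactly from the noncentral t with noncentrality d√n/√(2(1−r)).

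| Pairs | d (SD) | r | Non-paired | Paired |
|---|---|---|---|---|
| 20 | 0.5 | 0.3 | 46% | 57% |
| 20 | 0.5 | 0.5 | 45% | 70% |
| 20 | 0.5 | 0.7 | 44% | 87% |
| 20 | 0.3 | 0.5 | 16% | 36% |
| 20 | 0.8 | 0.5 | 88% | 96% |
| 50 | 0.5 | 0.5 | 88% | 97% |

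At r = 0 the two tests are nearly equal (46% and 45% at 20 pairs, d = 0.5). These are powers to detect any change, recovery included. They are not powers to detect a therapy effect.

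**4. Pairs for 80% power at d = 0.5 (normal approximation).**
- Non-paired: 2(1.645 + 0.842√(1−r))²/d², giving 45, 41 and 36 at r = 0.3, 0.5 and 0.7
- Paired: 2(1−r)(1.645 + 0.842)²/d², giving 35, 25 and 15

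The exact noncentral t raises the paired figures to 37, 27 and 17, so the approximation slightly flatters the paired test.

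**5. Whether a between-arm reading fits the schedule.** Early therapy starts at about one month and runs for four weekly sessions, so early-arm post-therapy scores fall near two months post-injury. Waitlist pre-therapy scores also fall near two months. Those are different people, and an independent-samples test would be correct for that contrast. The analysis sentence does not state it.

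**The case against.** The strongest reply is that the trial has two randomised arms, the sentence speaks of tests in the plural, and "one tailed, non-paired t-tests" may simply be the label for an early-versus-waitlist comparison. That could be early-arm post-therapy against waitlist pre-therapy scores near two months, or pre-to-post change compared between arms. Under either, the standard error is right and only the wording is loose. This stands as a possibility, which is why the standard-error fault is tied to the literal reading. It does not remove the point: the only comparison the sentence names is pre against post, and if a between-arm test was meant, the plan does not say so. The two between-arm versions also differ. Since both arms receive therapy, comparing their changes estimates an effect of timing.

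A second reply is that natural recovery is the larger problem, and that a paired test would detect recovery more readily without showing that therapy works. That is correct. It limits what the paired test achieves, and it limits the statement that false positives are not inflated to the null of no change.

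Third, every magnitude beyond the formula rests on assumed inputs. This also stands. The loss could be negligible with weak correlation, and is smaller with a large change or a large sample. The error can also be corrected at analysis.

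**Conclusion.** The concern holds. As written, the plan applies an independent-samples test to repeated scores from the same subjects and does not identify the contrast. That the sentence needs changing is certain under every reading; that the standard error is wrong depends on the literal, within-subject reading.

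On that reading, with positive correlation and equal variances, the error is conservative and its size is governed by the unknown r. Across r = 0.3 to 0.7, the worked case of 20 pairs and a 0.5 SD change loses between 11 percentage points of power (57 − 46) and 43 (87 − 44). The true loss in this trial cannot be fixed from the documents. This should be corrected before analysis. It is not a reason to doubt the data to be collected.

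**What to change.** Rewrite the analysis sentence so that it does the following:

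1. **Names each contrast**, with its arms and time points.
2. **For a therapy effect, states the early-versus-waitlist comparison explicitly**, for example early-arm post-therapy against waitlist pre-therapy scores, both near two months post-injury. Independent-samples methods are kept for this contrast only.
3. **For within-subject change, replaces the non-paired test** with a paired t-test on change or a mixed model with a subject effect. It should say that pre and post scores are matched by subject, and that this change alone does not separate therapy from natural recovery.

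The cost is a change of wording to one analysis sentence, with no added visits or measurements. The one practical requirement is that scores can be linked by subject, which the plan should state because the documents do not describe it.
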